9 STUDY DESIGN

9.1 OVERALL DESIGN

This RCT will enroll approximately 1000 participants with a self-reported diagnosis of chronic lower back pain (defined as moderate to severe pain lasting longer than three months) to test the efficacy of skills-based VR (EaseVRx) on long term pain management as an adjunct to traditional medical therapy. Enrolled participants will be randomized 1:1:1:1 and assigned to one of four treatment arms:

- 56-day skills-based VR program (EaseVRx-8w)
- 56-day skills-based VR program followed by an extended 56-day on-demand period (EaseVRx-8w plus extended on-demand)
- 56-day control (Sham VR-8w)
- 56-day control followed by an extended 56-day on-demand period (Sham VR-8w extended on-demand)

The primary outcome will be assessed using the BPI: an eight-item scale assessing pain intensity and pain interference on general activity, mood, walking ability, normal work, relations with other people, sleep, and enjoyment of life. Each participant's BPI score will be assessed immediately before the intervention, during the intervention, immediately following the intervention, and at 4-, 8-, 12-weeks, and 6-, 12-, 18-, and 24-months post intervention (see Schedule of Activities in Section 5.2).

Secondary outcomes include the Oswestry Disability Index score (ODI v2.1b), PROMIS Sleep Disturbance, PROMIS Depression, and PROMIS Anxiety that will be evaluated before the intervention, immediately following the intervention (Day 56 in all arms), 4-weeks post-treatment, 8-weeks post-treatment, 12-weeks post-treatment, 6 months post-treatment, 12 months post-treatment, 18 months post-treatment, and 24 months post-treatment. Participant Satisfaction will be evaluated at Day 56.

Additionally, participants will be administered the following surveys as tertiary and exploratory outcomes at the specified timepoints:

- Participant's Global Impression of Change Scale (PGIC): Day 56, 4-weeks post-treatment, 8-weeks post-treatment, 12-weeks post-treatment, 6 months post-treatment, 12 months post-treatment, 18 months post-treatment, and 24 months post-treatment

- Concerns About Pain (CAP-6) Scale: Baseline, Day 56, 4-weeks post-treatment, 8-weeks post-treatment, 12-weeks post-treatment, 6 months post-treatment, 12 months post-treatment, 18 months post-treatment, and 24 months post-treatment
- Systems Usability Scale (SUS): Day 56
- Behavioral Skills Use: Baseline, Day 56, 4-weeks post-treatment, 8-weeks post-treatment, 12-weeks post-treatment, 6 months post-treatment, 12 months post-treatment, 18 months post-treatment, and 24 months post-treatment
- Product Enhancement recommendations: Day 56 for the EaseVRx-8w and EaseVRx-8w plus extended on-demand groups, and at 8-weeks post-treatment for the EaseVRx-8w plus extended on-demand group
- Treatment Compliance: End of treatment for the EaseVRx and Sham VR groups and 8-weeks post treatment for the EaseVRx plus on demand Library and Sham VR plus on demand Library groups.

9.2 SCIENTIFIC RATIONALE FOR STUDY DESIGN

The use of the two active control groups (Sham VR-8w, Sham VR-8w extended on-demand arms) in this randomized control trial will minimize biases related to the novelty of the hardware and immersion.

9.3 JUSTIFICATION FOR DOSE

Based on previous research by AppliedVR and other researchers in the virtual reality therapeutic space, individuals have experienced success in pain management by using VR at least once daily, for 10-15 minutes, and as needed for breakthrough flares of pain. For those with significant career and family-related responsibility, AppliedVR recommends using the device once daily at night before bed.

9.4 END OF STUDY DEFINITION

The study will be considered complete at the time that the last participant performs the last survey. Participants are expected to remain in the study for 24 months after undergoing their respective treatment period (8 or 16 weeks). Participants who complete their 24-month follow-up survey (see Schedule of Activities, Section 5.2.) will be considered to have completed study participation.

10 SELECTION OF STUDY POPULATION

10.1 INCLUSION CRITERIA

In order to be eligible to participate in this study, an individual must meet all of the following criteria:

1. Male and female participants aged 18-85.
2. Self-reported diagnosis of chronic lower back pain.
3. Pain duration of at least three months.

4. Average pain intensity score of ≥ 4 and average pain interference score of ≥ 4 on the 0-10 BPI Pain Scale for the past month at screening.
5. Fluency in English.
6. Willing and able to comply with all study procedures including all required restrictions for the duration of study participation.
7. Able to give voluntary, written informed consent to participate and have signed an Informed Consent Form specific to this study.
8. Access to Wi-Fi for the duration of their study participation (24 months).
9. Access to a smartphone or computer for the duration of the study.
10. Availability of a physical mailing address that is not a PO box address for receipt of the device.
11. Completed the Baseline Survey plus at least two of the five sets of participant surveys that are administered during the 10-day pretreatment assessment period.
12. Able to provide photo ID.

10.2 EXCLUSION CRITERIA

An individual who meets any of the following criteria will be excluded from participation in this study:

1. Unable to understand the goals of the study due to cognitive difficulty.
2. Any medical condition that may prevent the use of virtual reality (e.g., current, or prior diagnosis of epilepsy, seizure disorder, hypersensitivity to flashing light or motion, migraines, any medical condition predisposing participant to nausea or dizziness, dementia, absence of stereoscopic vision or severe hearing impairment).
3. Injury to eyes, face, or neck that prevents comfortable use of VR.
4. Index back pain is linked to a cancer-related diagnosis.
5. Possible suicidal ideation as indicated by the 9th item of the participant Health Questionnaire-9 (PHQ-9).
6. Previous participation in the 2020 AVR EaseVRx pivotal study.
7. Receiving worker's compensation and/or involved in any active litigation related to an injury.
8. Current or recent participation (i.e., within the last 2 months) in any other research study involving a drug, device, vaccine, or other interventional treatment product; or plans to participate in another research study over the next 24 months.

10.3 PARTICIPANT RECRUITMENT AND SCREENING

Participants will be recruited for this decentralized virtual trial via two methods.

Method 1: participants diagnosed with chronic lower back pain will be recruited from physician referrals through the Sponsor's relationships with physicians who treat chronic lower back pain in adult populations within the United States. Physicians seeing participants who appear to be a good fit for the study will refer the participants to the study by providing them with a pamphlet that provides a link to the study website, where they will have an opportunity to learn more about the study. Participants will

then be directed to Curebase where they will be asked to create a user account. After the creation of such an account, participants will be able to take a brief Eligibility Survey. If eligible to participate, participants will be asked to go through the consenting process. During the next 10 days, participants will be required to complete their baseline survey and at least 2 out of 5 brief surveys to become eligible for randomization.

Method 2: AppliedVR will also use direct email marketing and social media advertising to make potential participants aware of the study. The email and social media advertisements will provide a link to the study website, where they will have an opportunity to learn more about the study. Potential participants will be redirected to Curebase to sign an e-consent form and take the Eligibility Survey.

The total number of participants that were pre-screened (prior to consent), screened (post consent), and screen failed, including the reasons for screen failure, will be captured automatically in Curebase. Research staff will be able to report on this as needed.

10.4 INFORMED CONSENT

After passing the screener survey, prospective participants will be directed to review and sign an electronic HIPAA, California Bill of Rights (if a participant is located in California, and an IRB-approved consent (eConsent) form prior to enrolling in the study. The eConsent form will explain the nature and scope of the study, the procedures to be performed as part of the study, the potential risks, and benefits of participation, expected duration of participation, possible treatment alternatives, and an overview of his/her rights as a study participant in lay terms. Participants will have the opportunity to discuss the study with their family or surrogates or think about it before agreeing to participate. Participants will be informed that participation is voluntary and will be assured that they may withdraw from the study at any time and for any reason, without repercussion. The HIPAA, California Bill of Rights, and eConsent process will be via the study dashboard (hosted by Curebase, Inc.).

After viewing the eConsent materials, participants will have an opportunity to email or call the research team with any questions they may have and will be given as much time as needed to receive answers before making a final decision regarding study participation. Participants will receive a telephone number, email, and will have access to contact support staff as needed.

When the individual is ready to confirm their willingness to participate, an electronic signature will be collected to complete the eConsent formalities. The participant will receive a copy of the fully signed HIPAA, California Bill of Rights, and eConsent forms via email to retain for their records, and a digital copy will be retained within the Curebase system as part of the study records.

10.5 SCREEN FAILURES

A screen failure is a participant who consents but does not receive any of the study interventions due to withdrawing consent, being withdrawn from the study, or not meeting eligibility requirements for treatment.

If a participant signs the eConsent form but is found ineligible for inclusion in the study prior to or during the initiation of the study intervention, the participant will not be advanced any further in this clinical investigation and will be listed as a screen failure. The participant will be notified and the participant's signed eConsent form and updated inclusion/exclusion criteria details will be retained by the research team.

A minimal set of screen failure information is required to ensure transparent reporting of screen failure participants, to meet the Consolidated Standards of Reporting Trials (CONSORT) publishing requirements and to respond to queries from regulatory authorities. Minimal information includes demography, screen failure details, eligibility criteria, and any serious adverse event (SAE).

To collect data related to CONSORT requirements, a Screening and Enrollment Log will be maintained. A research team member will review automated data from the eligibility survey on the Curebase dashboard.

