11.2 ENROLLMENT & RANDOMIZATION

Curebase will automatically direct the participant to a survey to provide a shipping address before participants complete the Baseline Survey assessments and two out of five sets of BPI surveys. Once the second BPI survey is filled out, the participant will be randomized into an arm of the study in 1:1:1:1 via Curebase and assigned a Participant ID number. The AppliedVR research team will arrange a device shipment based on the randomization assignment, and Curebase will notify the participant of the shipment tracking details.

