1.8 STUDY ANALYSIS SETS

1.8.1 INTENT TO TREAT ANALYSIS SET (ITT)

All subjects randomized will be included in the intent-to-treat (ITT) Analysis Set. The ITT analysis will only be considered a supportive and complementary analysis.

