1.8.2 MODIFIED INTENT TO TREAT ANALYSIS SET (mITT)

For the primary analysis and safety evaluations, the mITT Analysis Set will be defined and presented as primary. The mITT Analysis Set includes all enrolled subjects who actually receive the device. If all enrolled subjects receive the device, the mITT and ITT Analysis Sets will coincide and will be referred to as the ITT Analysis Set.

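### Protocol 10.5 lets a randomised participant be listed as a screen failure and stopped, although the SAP counts that person in ITT and, once the device is received, in the primary mITT set

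*Protocol*

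**What the plan says.** **Order of events.** Protocol 11.2: "Once the second BPI survey is filled out, the participant will be randomized into an arm of the study". The sponsor's team then ships the device according to the assigned arm.

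**Screen failure.** Protocol 10.5 opens with: "A screen failure is a participant who consents but does not receive any of the study interventions", the reasons being withdrawal of consent, being withdrawn, or ineligibility. Its second paragraph goes further. It covers anyone who has signed consent and turns out not to qualify, whether this emerges before treatment starts or while it is being started. For such a person the rule is: "the participant will not be advanced any further in this clinical investigation and will be listed as a screen failure". The minimal information it names for screen failures is demographics, the screen-failure particulars, the eligibility criteria and any SAE. No BPI follow-up is mentioned.

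**Analysis sets.** SAP 1.8.1: "All subjects randomized will be included in the intent-to-treat (ITT) Analysis Set"; this set is supportive only. SAP 1.8.2, the primary set for efficacy and safety: "The mITT Analysis Set includes all enrolled subjects who actually receive the device". SAP 1.8.3 removes participants with important eligibility violations from the per-protocol set and from no other.

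**Neighbouring rules.** Protocol 13.1 says that stopping the device does not by itself end study participation and that the remaining procedures should be completed. Protocol 13.2 lets an investigator withdraw a participant whose exclusion criterion comes to light late, and has an SAE arising from an undisclosed disqualifying condition documented as an eligibility deviation. Protocol 16.4 collects all adverse events from the first time the headset is put on.

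**The concern.** Screening normally closes at randomisation. Here it closes at receipt or start of the intervention, so the whole interval from allocation through shipping to first use lies inside the screen-failure definition. A participant who has been randomised, and may already hold the device, can be stopped under a label meant for people who never entered the trial.

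Three things are at stake. Week 8 outcomes would be missing for people whom the SAP intends to analyse. Non-serious events at first use, such as cybersickness, could go unrecorded for someone stopped at that moment, although SAP 3.2 bases safety on mITT. And an exclusion made after allocation is not protected by randomisation. Exclusion criteria 2 and 3 include motion hypersensitivity, conditions predisposing to nausea or dizziness, and comfort in the headset. These could first surface at first use, where the arms differ (immersive 3D against 2D footage).

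**Working it through.** **1. Sequence.** Consent, then baseline survey, then second BPI survey and randomisation (11.2), then shipment by arm (11.2), then receipt, then initiation. The first sentence of 10.5 closes screening at receipt of an intervention and its second paragraph closes it during initiation. Both come after randomisation, and no section limits screen failure to people not yet randomised.

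**2. The rules side by side for randomised participants.**

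| Randomised participant | Protocol 10.5 | SAP 1.8 | Protocol 13 |
|---|---|---|---|
| Withdraws consent before the kit arrives | Screen failure | ITT; not mITT | Withdrawal (13.2) |
| Found ineligible before the kit arrives | Screen failure, stopped | ITT; not mITT | Possible investigator withdrawal (13.2) |
| Found ineligible during initiation | Screen failure, stopped | ITT and mITT; out of PP only | Possible withdrawal (13.2); follow-up continues if only the device is stopped (13.1) |

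The last row also sets 10.5 against itself: the opening sentence requires that no intervention was received, while the second paragraph reaches into initiation. The mITT definition speaks of enrolled subjects without defining enrolment, so a late screen failure could be argued to be either in or out.

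**3. Outcomes the rule itself loses.** In the first row, outcomes are lost under any wording, because consent has gone. The avoidable loss is in the second and third rows. Only the third touches the primary analysis.

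**4. Number of people.** The documents give no rate of screen failure after randomisation. Assume 1% to 10% of the planned 1000: 1000 × 0.01 = 10; × 0.02 = 20; × 0.05 = 50; × 0.10 = 100. This covers all three rows together; nothing in the documents allows the mITT part to be separated.

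**5. Power.** Inputs from SAP 2.8.1: Intensity difference 0.91, SDs of change 1.64 and 1.68, 120 per group, 15% loss, 33% claims match.

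- SD = √((1.64² + 1.68²)/2) = 1.66.
- Power ≈ Φ(0.91 / (SD × √(2/n)) − 2.241), Intensity alone at two-sided 0.025.
- The plan's own figure first: with n = 120, 4.246 − 2.241 ≈ 2.00, giving 97.7%. Simulating both endpoints with Hochberg at one-sided 0.025 gives about 98%. Both agree with the stated figure of more than 95%.
- The plan's sample size: 240 / 0.33 / 0.85 = 855.6 (stated 855), and 855 + 145 = 1000.

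Now take a fraction q out of 1000 and apply the SAP's loss and match rates, n per group = 1000 × (1 − q) × 0.85 × 0.33 / 2:

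| q | n per group | Power |
|---|---|---|
| 0% | 140.3 | 99.1% |
| 5% | 133.2 | 98.7% |
| 10% | 126.2 | 98.3% |

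Without the claims-match restriction, power exceeds 99.9% throughout.

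**6. Scale of a possible shift.** If those removed would have shown no treatment difference (an assumption), the all-randomised Intensity difference would be 0.91 × 0.95 = 0.86 at 5% and 0.91 × 0.90 = 0.82 at 10%. For Interference it would be 0.74 × 0.95 = 0.70 and 0.74 × 0.90 = 0.67. This shows dilution only. The documents give no basis for sizing a bias from removals that differ by arm.

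**The case against.** The strongest reply is that 10.5 sets a label, a stop and a minimal data set but never mentions ITT or mITT. Protocol 17 refers all statistical matters to the SAP, which is categorical that everyone randomised is in ITT. That stands, and it rules out several readings a reader might infer:

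- *That 10.5 deletes people from the analysis sets.* It does not say so. It stops their data, which leaves the SAP's sets intact on paper with avoidable gaps in them.
- *That the CONSORT flow will understate the number randomised.* Randomisation and Participant ID are recorded in Curebase, and 10.5 requires a log for CONSORT purposes. Mislabelling is a risk; an undercount is not shown.
- *That the ITT analysis cannot be run.* SAP 2.9.3 would impute people with no follow-up from baseline data, which these participants have. SAP 2.9.2 says the opposite, but that is a separate inconsistency.
- *That the opening definition damages the primary analysis.* On its own it covers people who never receive a device. They are outside mITT by definition, and ITT is only supportive. The link to mITT rests on the words about initiation in the second paragraph.
- *That removals will differ by arm.* Initiation is undefined and may mean no more than set-up, participants are blinded, and many criteria are baseline facts. Against this, the documents do not say who decides eligibility after randomisation, and Protocol 12.1 does not list the team that ships by arm among those blinded. A difference is possible, not demonstrated.

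It is also fair that eligibility is surveyed before randomisation, so late-found ineligibility should be uncommon. What remains is that 10.5 prescribes a stop for participants whom SAP 1.8.1 and 1.8.2 count and whom Protocol 13 handles in other ways.

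**Conclusion.** The point holds as a contradiction between a stated rule and the analysis sets. Applied literally, Protocol 10.5 ends data collection for some randomised participants who belong to ITT and, if they have the device, to the primary mITT set. The consequence is avoidable missing outcomes and possibly missing non-serious adverse events, with a bias that is possible but cannot be sized from the documents.

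The number affected is unknown. The range of 10 to 100 among 1000 rests on an assumed 1% to 10%, includes people who withdraw consent, and mostly concerns the supportive set; the mITT part is probably small. Intensity power stays at 98% or above even at 10% within the claims-matched subset, so this is not a sample-size problem. Exclusion from the analysis sets and an understated randomised count should be described as risks of the wording, not as what the plan provides. The text should be corrected because the remedy is cheap and protects the comparison against exclusions made after allocation.

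**What to change.** Amend Protocol 10.5 so that a screen failure is a person who consents but is not randomised. Add that every randomised participant:

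- stays in ITT, and in mITT if the device was received;
- is counted as randomised in the CONSORT flow;
- is sent the scheduled surveys unless consent is withdrawn, whether or not device use continues;
- has ineligibility found after randomisation recorded as a protocol deviation, with adverse events collected as in 16.4 once the headset has been used.

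Define enrolled in SAP 1.8.2, and reconcile Protocol 10.5, 13.1 and 13.2 with SAP 1.8.1 and 1.8.2. This concerns counting and data collection only. Whether such a person goes on using the device is a clinical matter on which the sections need to be made consistent.

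The cost is a wording amendment and a few extra automated surveys.

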11 STUDY PROCEDURES

11.1 BASELINE SURVEY

After signing the eConsent form, participants will automatically be directed to complete a set of Baseline survey assessments that will include the following:

- Brief Pain Inventory - intensity/interference
- Oswestry Disability Index
- PROMIS Sleep Disturbance
- PROMIS Depression
- PROMIS Anxiety
- Concerns About Pain (CAP-6) Scale
- Behavioral Skills Use

Reminders will be sent approximately 1 hour and 24 hours after starting a survey to encourage the completion of Baseline surveys.

Twenty-four hours after completing the Baseline survey assessments, participants will be contacted with information about completing an optional incentivized set of surveys that include the following:

- Pain Self-Efficacy Questionnaire (PSEQ-10)
- Multidimensional Assessment of Interoceptive Awareness (Version 2)
- Multidimensional Health Locus of Control

Reminders will be sent approximately 1 hour and 24 hours after starting a survey to encourage optional survey completion.

Participants who filled out the Baseline Survey assessments will be contacted via an automated Curebase email/text to fill out at least 2 out of 5 pre-treatment BPI surveys over the next 9 days. Note: Completion of these surveys is a pre-requisite for randomization.

11.2 ENROLLMENT & RANDOMIZATION

Curebase will automatically direct the participant to a survey to provide a shipping address before participants complete the Baseline Survey assessments and two out of five sets of BPI surveys. Once the second BPI survey is filled out, the participant will be randomized into an arm of the study in 1:1:1:1 via Curebase and assigned a Participant ID number. The AppliedVR research team will arrange a device shipment based on the randomization assignment, and Curebase will notify the participant of the shipment tracking details.

